3.3.5 Renal and Hepatic Function

- a. Renal function: Patient's serum creatinine must be ≤ 1.5 x institutional upper limit of normal (ULN) according to age. If the serum creatinine is greater than 1.5 times normal, the patient must have a calculated creatinine clearance or radioisotope

GFR \geq 70mL/min/1.73m². Alternatively, a 24-hour creatinine clearance may also be used.

1. Pediatric Population (age <18): Calculated creatinine clearance \geq 70 ml/min/1.73m² as calculated by the Schwartz formula for estimated glomerular filtration rate (GFR) where $GFR (ml/min/1.73 m^2) = k * Height (cm) / serum creatinine (mg/dl)$. k is a proportionality constant which varies with age and is a function of urinary creatinine excretion per unit of body size; 0.45 up to 12 months of age; 0.55 children and adolescent girls; and 0.70 adolescent boys.
 2. Adult Population (age \geq 18): If serum creatinine $> 1.5 \times$ ULN, then the estimated glomerular filtration rate (GFR) must be > 70 mL/min/1.73 m² as calculated by the Modification of Diet in Renal Disease equation where Predicted GFR (ml/min/1.73 m²) = 186 x (Serum Creatinine)^{-1.154} x (age in years)^{-0.023} x (0.742 if patient is female) x (1.212 if patient is black).
- b. Hepatic function: ALT and AST must be $< 5 \times$ institutional upper limit of norm ULN. Total bilirubin must be $\leq 1.5 \times$ ULN (except in the case of subjects with documented Gilbert's disease $\leq 5 \times$ ULN).

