3.3.1 Age

Patients must be ≥ 1 and ≤ 21 years of age at the time of enrollment.

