6.4 Methotrexate (MTX, AMETHOPTERIN) NSC #740 (112004)

6.4.1 Source and Pharmacology:

A folate analogue which inhibits the enzyme dihydrofolate reductase, halting DNA, RNA, and protein synthesis. Initial IV half-life is about 1.2 hours, with a second phase of 10.4 hours. About 50% is bound to protein. Transport into the cell is carrier-mediated. Once in the cell, MTX (Glu)_n are formed, the number of which are related to the cytotoxic effect. Once MTX (Glu)_n are formed, they do not pass back out of the cell unless converted back to MTX. After oral administration, about 60% of a 30 mg/m² dose is rapidly absorbed from the GI tract, with peak blood levels at 1 hour. Above this dose, absorption decreases significantly. Absorption can be very erratic, varying between 23% and 95%. A 20-fold difference between peak levels of drug has been reported (0.1 to 2mM). There is significant enterohepatic circulation of MTX: 9% of MTX is excreted in feces. MTX is excreted unchanged in the urine, except at high doses when it is partially metabolized to hydroxy-MTX and excreted.

6.4.2 Toxicity:

	Common Happens to 21-100 children out of every 100	Occasional Happens to 5-20 children out of every 100	Rare Happens to <5 children out of every 100
Immediate: Within 1-2 days of receiving drug	Nausea, headache	Arachnoiditis: (headache, fever, vomiting, meningismus, nuchal rigidity, and pleocytosis)	Anaphylaxis, vomiting, seizures(L), confusion, back pain, rash, bleeding into subarachnoid or subdural space (risk > with platelet counts < 20,000),

	Common Happens to 21-100 children out of every 100	Occasional Happens to 5-20 children out of every 100	Rare Happens to <5 children out of every 100
Prompt: Within 2-3 weeks, prior to the next course			Myelosuppression, ataxia, somnolence, cranial nerve palsy, subacute myelopathy (paraparesis/paraplegia), speech disorders, pain in the legs, bladder dysfunction
Delayed: Any time later during therapy, excluding the above conditions		Learning disability (L), Cognitive disturbance	Leukoencephalopathy ¹ (L)
Late: Any time after completion of treatment			Progressive CNS deterioration ¹
Unknown Frequency and Timing: Fetal and teratogenic toxicities:			

¹ May be enhanced by HDMTX and/or cranial irradiation. (L)
 Toxicity may also occur later.

6.4.3 Formulation and Stability:

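### Section 3.3.5 prints the adult GFR equation with an age exponent of -0.023, which makes the 70 mL/min/1.73 m² limit looser from age 18 than just before it; check the exponent against its source

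*Combined protocol and SAP*

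**What the plan says.** Section 3.3.5(a) accepts a serum creatinine up to 1.5 x ULN for age. Above that a GFR of 70 mL/min/1.73 m² is needed: "If the serum creatinine is greater than 1.5 times normal, the patient must have a calculated creatinine clearance or radioisotope" GFR at that level. A measured route is also open: "Alternatively, a 24-hour creatinine clearance may also be used".

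The estimate depends on age:

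- **Under 18:** k x height / creatinine, with k of "0.55 children and adolescent girls; and 0.70 adolescent boys". The limit is at least 70.
- **18 and over:** "as calculated by the Modification of Diet in Renal Disease equation where Predicted GFR" is 186 x creatinine^-1.154 x age^-0.023, with factors "0.742 if patient is female) x (1.212 if patient is black". The limit is strictly above 70.

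Section 3.3.1 caps enrollment at "21 years of age at the time of enrollment", so the adult equation serves ages 18 to 21 only. Section 3.3 has sites apply the criteria as written, with no waivers. The exponent is printed once. The documents contain no worked example, computed GFR or creatinine cut-off to test it against.

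**The concern.** An exponent of -0.023 leaves almost no age effect in an equation that carries an explicit age term, so a misprint is a natural suspicion. The printed equation also lets a patient fail the limit at 17 and pass it at 18 with the same creatinine and height.

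Because waivers are not allowed, a site has no room to correct a wrong constant. Every cohort receives methotrexate, intrathecal in A and B and oral in C with intrathecal doses as needed. Section 6.4.1 says "MTX is excreted unchanged in the urine, except at high doses". Phase I has 6 evaluable patients per cohort and dose level, and section 9.2 considers de-escalation when more than 1 of the first 6 is treated unsuccessfully. In groups that small, one patient admitted through a wrong formula could matter.

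**Working it through.** The plan gives no computed figure to reproduce, so the check evaluates its two printed formulas directly.

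**Inputs from section 3.3.5:** 186; exponents -1.154 and -0.023; factors 0.742 (female) and 1.212 (Black); k = 0.70 (adolescent boys) and 0.55 (girls); limit 70. **From section 3.3.1:** upper age 21.

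**Assumptions (not in the documents):** heights of 175 cm (range 160 to 190) for males and 163 cm (range 150 to 180) for females; the ULN, varied below and taken as equal on both sides of 18; any comparator exponent. The 1.5 x ULN condition is read as governing both age branches. Results are for non-Black patients unless stated.

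**1. Age term.** 18^-0.023 = 0.9357 and 21^-0.023 = 0.9324, a change of -0.35%.

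**2. Creatinine at which GFR = 70.**

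- Adult, age 18: (186 x 0.9357 x f / 70)^(1/1.154). Male (f = 1): 2.20 mg/dL. Female (f = 0.742): 1.70 mg/dL. With the 1.212 factor: 2.60 and 2.01.
- Under 18: k x height / 70. Boy: 0.70 x 175 / 70 = 1.75. Girl: 0.55 x 163 / 70 = 1.28.
- The cut-offs coincide only at 2.202 x 70 / 0.70 = 220 cm (male) or 1.700 x 70 / 0.55 = 216 cm (female). Below those heights the adult branch is looser.

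**3. Same patient, either side of 18.**

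- Male, 175 cm, creatinine 2.0: 0.70 x 175 / 2.0 = 61 (fails), then 186 x 2.0^-1.154 x 0.9357 = 78 (passes).
- Female, 163 cm, creatinine 1.6: 0.55 x 163 / 1.6 = 56 (fails), then 186 x 1.6^-1.154 x 0.9357 x 0.742 = 75 (passes).

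**4. Size of the jump.** Printed adult GFR at age 18, at the creatinine where the pediatric formula gives exactly 70:

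| Sex, height | Creatinine | Adult GFR | Excess over 70 |
|---|---|---|---|
| Male, 160 cm | 1.60 | 101 | 45% |
| Male, 175 cm | 1.75 | 91 | 30% |
| Male, 190 cm | 1.90 | 83 | 19% |
| Female, 150 cm | 1.18 | 107 | 53% |
| Female, 163 cm | 1.28 | 97 | 39% |
| Female, 180 cm | 1.41 | 87 | 24% |

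**5. Who is affected.** The estimate is used only above 1.5 x ULN, so the mismatch band runs from the larger of the pediatric cut-off and 1.5 x ULN up to the adult cut-off.

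- 175 cm male: ULN 1.0 gives 1.75 to 2.20; ULN 1.2 gives 1.80 to 2.20; the band is empty from 2.20 / 1.5 = 1.47.
- 163 cm female: ULN 0.8 gives 1.28 to 1.70; ULN 1.0 gives 1.50 to 1.70; the band is empty from 1.70 / 1.5 = 1.13.

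**6. If another exponent e was intended.** The printed formula overstates GFR by age^(-0.023 - e) - 1:

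| Assumed e | Age 18 | Age 21 |
|---|---|---|
| -0.10 | 25% | 26% |
| -0.15 | 44% | 47% |
| -0.203 (digits transposed) | 68% | 73% |
| -0.25 | 93% | 100% |

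**7. Would -0.203 make the branches agree?** No. The age-18 cut-offs would become 1.40 (male) and 1.08 (female), stricter than 1.75 and 1.28. A 175 cm male with creatinine 1.6 would score 0.70 x 175 / 1.6 = 77 at 17 (passes) and 60 at 18 (fails). For that height the formulas meet at the pediatric cut-off when e = ln(70/97.5) / ln 18 = -0.115, where 97.5 = 186 x 1.75^-1.154.

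**The case against.** The strongest reply is that the documents do not establish an error. They name the equation but give no other value for its age exponent, and two different estimating formulas need not meet at 18. This stands, and it limits what can be claimed:

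- A reader might infer that -0.023 is certainly a transposed -0.203 and that GFR is inflated by about 70%. Nothing in the documents supplies -0.203, and the overstatement runs from 25% to 100% over the exponents tried. The mismatch that rests on the printed formulas is about 30% to 39% at the assumed heights.
- A reader might infer that -0.203 would restore agreement, because it also rejects the 175 cm male with creatinine 2.0 (GFR 46). Step 7 shows that the mismatch reverses at lower creatinine. The discontinuity therefore cannot identify the right exponent.
- A reader might infer that unsuitable patients were enrolled or that toxicity counts were distorted. The documents show no patient who qualified this way. Methotrexate is scheduled only intrathecally in Cohorts A and B, and section 6.3.1 puts renal excretion of mitoxantrone at 11% of the dose.

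The group is also narrow, and radioisotope GFR or a 24-hour clearance can replace the estimate. The difference between at least 70 and above 70 is negligible for a continuous quantity.

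The reply does not remove the conflict between the printed branches, or the doubt about a constant that sites must apply as printed.

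**Conclusion.** The point holds as a request to verify a suspect constant in a binding criterion. The printed exponent makes age almost inert, and the printed adult branch passes patients whom the same limit rejects just before 18. The creatinine cut-off moves from 1.75 to 2.20 mg/dL (male) and from 1.28 to 1.70 (female), a rise of 0.45 and 0.42 mg/dL. These figures rest on the printed formulas and the assumed heights.

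That the exponent is a misprint remains probable rather than shown, and the 68% to 73% overstatement is conditional on -0.203. The practical reach is small: ages 18 to 21, creatinine above 1.5 x ULN, no measured GFR. For non-Black patients the mismatch disappears if the ULN is at least about 1.47 (male) or 1.13 (female) mg/dL. With the 1.212 factor those limits are 2.60 / 1.5 = 1.73 and 2.01 / 1.5 = 1.34. Any effect on the dose-level decisions is possible but cannot be quantified from the documents.

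**What to change.** 1. Confirm the superscript on the page, check the age exponent in section 3.3.5(a)(2) against the source of the named equation, and correct it if the digits were transposed.
2. State the limit with one inequality in the general, pediatric and adult text.
3. Re-check any enrolled patient aged 18 or over who qualified through this formula.
4. Do not choose an exponent to force the two formulas to meet at 18; they need not coincide even after correction. If a step at 18 remains, acknowledge it in the text.

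The cost is one line in an amendment and a short eligibility check. The downside is small: if the exponent is corrected to a more negative value, a few young adults with raised creatinine may no longer qualify by estimate and would need the radioisotope or 24-hour route that the section already allows.

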3.3.6 Cardiac Function

Patients must have a shortening fraction $\geq 27\%$ or an ejection fraction $\geq 55\%$ by echocardiogram, cardiac MRI or MUGA.

3.3.7 Reproductive Function

- a. Female patients must not be pregnant and those of childbearing potential must have a negative urine or serum pregnancy test confirmed within one week prior to enrollment.
- b. Female patients with infants must agree not to breastfeed their infants while on this study.
- c. Male and female patients of childbearing potential must agree to use an effective method of contraception during the study.

3.4 Exclusion Eligibility Criteria

3.4.1 Active CNS disease (CNS 3) is exclusionary. Patients with CNS 1 or CNS 2 disease may be enrolled, which is inclusive of patients with a recent history of CNS3 disease which is now resolved to CNS1 or CNS2

3.4.2 Patients will be excluded if they have any isolated extramedullary disease, including isolated testicular or isolated CNS disease.

3.4.3 Patients will be excluded if they have previously received Marqibo®.

- 3.4.4** Patients will be excluded if they have a known allergy to any of the drugs used in the study, with the exception that patients with an allergy to pegaspargase who can receive Erwinia asparaginase are eligible. Patients unable to receive any formulation of asparaginase may only enroll on cohort C
- 3.4.5** Patients will be excluded if they have active, uncontrolled systemic fungal, bacterial, viral or other infection despite appropriate antibiotics or other treatment.
- 3.4.6** Patients who require azole antifungal agents will be excluded. Azoles must be discontinued at least one week prior to the start of Marqibo®.
- 3.4.7** Patients will be excluded if there is a plan to administer non-protocol chemotherapy, radiation therapy, another investigational agent or immunotherapy during the study period.
- 3.4.8** Patients with pre-existing, persistent grade 2 or greater sensory or motor neuropathy from any cause will be excluded. (Patients on chronic stable doses of gabapentin or similar agents for history of neuropathy may be included if there are no active neuropathic symptoms)
- 3.4.9** Patients will be excluded if they have significant concurrent disease, illness, psychiatric disorder or social issue that would compromise patient safety or adherence with the protocol treatment or procedures or interfere with consent, study participation, follow up, or interpretation of study results.
- a. Patients with Down syndrome will not be eligible for enrollment on Cohort A
- 3.4.10** Patients with a known history human immunodeficiency virus (HIV) will be excluded due to the increased risk of complications such as severe infection and unknown interaction of Marqibo® with antiretroviral drugs.
- 3.4.11** Active hepatitis B or C infection as defined by seropositive for hepatitis B (hepatitis B surface antigen (HBsAg)) or hepatitis C and elevated liver transaminases (defined as above the ULN per the institution normal ranges).

3.5 Regulatory

3.5.1 Informed Consent

All patients and/or their parents or legal guardians must sign a written informed consent. Age appropriate assent will be obtained per institutional guidelines. To allow non-English speaking patients to participate in this study, bilingual health services will be provided in the appropriate language when feasible.

3.5.2 Protocol Approval

All institutional, FDA, and NCI requirements for human studies must be met.

4.0 TREATMENT PROGRAM

The following sections detail the treatment plan for the therapy. Please refer to the Drug Information section for additional administration guidelines. Treatment should begin within three calendar days of enrollment.

There are 3 treatment cohorts on this protocol. Please see protocol sections 2.4.1 and 2.4.2 for review of the experience to date on this protocol.

There will be no inpatient dose escalation or de-escalation.

4.1 Treatment Course

Only 1 course of treatment will be permitted. Upon completion of treatment on this study, plans for additional therapy will be at the discretion of the treating team.

As of Amendment 3, cohorts A and B will be treating at dose level 1; Cohort C will be treating at dose level 2.

Marqibo Dose Levels

Dose Level 1: 1.5 mg/m²

Dose Level 2: 2.0 mg/m²

Cohort A:

	Day 1	Day 2	Day 3	Day 4	Day 5	Day 8	Day 15	Day 16	Day 17	Day 18	Day 19	Day 22	Day 29
Marqibo®	●					●	●					●	Response Evaluator
Dexamethasone	●	●	●	●	●		●	●	●	●	●		
Mitoxantrone	●	●											
Pegaspargase#			●						●				
IT Methotrexate	●					●							

asparaginase Erwinia chrysanthemi (Erwinaze®), crisantapase (Erwinase®) asparaginase Erwinia chrysanthemi (recombinant)-rywn (Rylaze®) may be substituted for allergy to Pegaspargase. See below.

Drug Administration Order

Marqibo will be administered first. Mitoxantrone will follow Marqibo administration on day 1 with dexrazoxane to be given immediately before mitoxantrone (when dexrazoxane is utilized [optional]). Timing of IT methotrexate is flexible in regards to the timing of Marqibo, but should not be given simultaneously in order to reduce the risk of administration route error.

Marqibo® (Dose level 1 only as of Amendment 3)

- Dose Level 1: 1.5 mg/m²/dose (no dose cap) given IV over 60 minutes (±10 minutes) on days 1, 8, 15 and 22.
- ~~Dose Level 2: 2 mg/m²/dose (no dose cap) given IV over 60 minutes (±10 minutes) on days 1, 8, 15 and 22.~~
- Review list of concomitant medications that are prohibited (CYP3A4 inhibitors) or to be used with caution (Appendix 3). See section 4.5 for drug interactions.
- Dose will be given over 60 minutes ± 10 minutes

Dexamethasone

- 20 mg/m²/day divided BID given orally on days 1 through 5 and 15 through 19. The two doses should be separated by at least 8 hours
- Any oral formulation of dexamethasone is acceptable
- IV may be given if oral formulation is not tolerated (please document reason or al could not be given)

Mitoxantrone

- 10 mg/m²/day given on days 1 and 2 as a short IV infusion over 5-15 minutes. Do not infuse over less than 3 minutes.
- Dose will be given over 5-15 minutes
- See section 5.6 for guidance on optional cardioprotection.

Pegaspargase

- 2,500 international units/m²/day IM or IV on days 3 and 17. **(Cap individual dose at 3,750 IU, based on vial size)**
- If available and FDA approved, asparaginase Erwinia chrysanthemi (Erwinaze®), asparaginase Erwinia chrysanthemi (recombinant)-rywn (Rylaze®) or crisantapase (Erwinase®) may be substituted for pegaspargase in patients with systemic allergic reaction.
- o Asparaginase Erwinia chrysanthemi (Erwinaze®) or Cristantapase (Erwinase®): May be dosed per package insert guidelines as 25,000 IU/m²/dose IM or IV over 1-2 hours. Give 6 doses of asparaginase Erwinia chrysanthemi (Erwinaze®) or Cristantapase (Erwinase®) over 2 weeks on a schedule of every other day (for example, q 48 hours, or M/W/F dosing) for each dose of planned pegaspargase.

- o Erwinia chrysanthemi (recombinant)-rywn (Rylaze®): Refer to current FDA product information for dosing at the time of product administration.
- o For any Erwinia formulation, **each individual dose not to exceed pegaspargase equivalent dosing of 3,750 IU (i.e., cap individual dose at 37,500 IU Erwinia)**. Route of administration, dose schedule and total doses administered should be documented, as this could contribute to variability in PK data for Marqibo®.
- Dose may be administered by IM or IV per product information guidelines (Please document route of administration).
- Premedications may be given per institutional standard.

Intrathecal methotrexate

- Given intrathecally to all patients the dose defined by age below on days 1 and 8 (+ 2 days). *Note:* The “Day 1” intrathecal chemotherapy dose may be given during eligibility screening evaluation within two weeks prior to Day 1 chemotherapy, and does not need to be repeated on Day 1. Alternatively, per standard of care, ARA-C and hydrocortisone may be substituted if methotrexate is contraindicated.
- IT methotrexate may also be given at day 29 (+/- 2 days) during disease assessment
- Timing of IT methotrexate is flexible in regards to timing of Marqibo®. However, these agents should not be given simultaneously in order to reduce the risk of administration route error.

Age (years)	Methotrexate (mg)
1-1.99	8 mg
2-2.99	10 mg
3-8.99	12 mg
≥ 9	15 mg

Cohort B: ALL R3/Marqibo without anthracycline

	Day 1	Day 2	Day 3	Day 4	Day 5	Day 8	Day 15	Day 16	Day 17	Day 18	Day 19	Day 22	Day 29	Response Evaluator	
Marqibo®	●					●	●						●		
Dexamethasone	●	●	●	●	●		●	●	●	●	●				
Pegaspargase[#]			●						●						
IT Methotrexate	●					●									

Asparaginase Erwinia chrysanthemi (Erwinaze®), crisantapase (Erwinase®) asparaginase Erwinia chrysanthemi (recombinant)-rywn (Rylaze®) may be substituted for allergy to Pegaspargase. See below.

Drug Administration Details:

As per Cohort A, without mitoxantrone

Marqibo®

- Dose Level 1: 1.5 mg/m²/dose (no dose cap) given IV over 60 minutes (±10 minutes) on days 1, 8, 15 and 22.
- Dose Level 2: 2 mg/m²/dose (no dose cap) given IV over 60 minutes (±10 minutes) on days 1, 8, 15 and 22.
- Review list of concomitant medications that are prohibited (CYP3A4 inhibitors) or to be used with caution (Appendix 3). See section 4.5 for drug interactions.
- Dose will be given over 60 minutes ± 10 minutes

Other agents and instructions as detailed above in Cohort A, without mitoxantrone.

Cohort C: Modified Maintenance with Marqibo®

	Day 1	Day 2	Day 3	Day 4	Day 5	Day 8	Daily through day 13	Day 14
Marqibo®	●							Response Evaluator
Dexamathasone	●	●	●	●	●			
Methotrexate (PO)	●					●		
Mercaptopurine (PO)	●	●	●	●	●	●	●	
IT Methotrexate as needed no more than once weekly								

Marqibo®

- Dose Level 1: 1.5 mg/m²/dose (no dose cap) given IV over 60 minutes (±10 minutes) on day 1.
- Dose Level 2: 2 mg/m²/dose (no dose cap) given IV over 60 minutes (±10 minutes) on day 1.
- Review list of concomitant medications that are prohibited (CYP3A4 inhibitors) or to be used with caution (Appendix 3). See section 4.5 for drug interactions.
- Dose will be given over 60 minutes ± 10 minutes

Dexamethasone

- 6 mg/m²/day divided BID given orally on days 1 through 5. The two doses should be separated by at least 8 hours

- Any formulation of dexamethasone is acceptable

Methotrexate

- 20 mg/m²/dose given orally on day 1 and day 8.

Mercaptopurine

- 75 mg/m²/dose/day given orally, daily from days 1-13.

Intrathecal methotrexate

- Given intrathecally as needed, but no more than once weekly. Age-based dosing as below. Alternatively, per standard of care, ARA-C and hydrocortisone may be substituted if methotrexate is contraindicated.
- Timing of IT methotrexate is flexible in regard to timing of Marqibo®. However, these agents should not be given simultaneously in order to reduce the risk of administration route error.

Age (years)	Methotrexate (mg)
1-1.99	8 mg
2-2.99	10 mg
3-8.99	12 mg
≥ 9	15 mg

See appendix 8 for starting dose guidelines.

Dose modifications: (for patients without pre-existing disease related cytopenia)

If neutrophil count falls below 500/mcL or if platelet count falls below 50,000/mcL during cohort C, mercaptopurine will be held until recovery of neutrophil count above 750/mcL and platelets > 75,000/mcL.

For the first drop in ANC or platelets, resume MP at the same dose the patient was taking prior to the episode of myelosuppression.

If neutrophil count falls below 500/mcL or if platelet count falls below 50,000/mcL for a second (or greater) time, discontinue doses of MP

In the setting of liver dysfunction, with 6MP and oral methotrexate:

For increase in hepatic transaminases (SGPT/ALT or SGOT/AST) to greater than 5x ULN (Grade 3 toxicity), obtain total and direct bilirubin. Monitor SGPT/ALT, SGOT/AST and total and direct bilirubin as long as transaminases remain over 5x ULN.

Continue full dose therapy unless either of the following occurs:

- Direct bilirubin > 2 mg/dL

- SGPT/ALT or SGOT/AST > 20x ULN (Grade 4 toxicity) ~~on 2 determinations at least 1 week apart.~~
- If either of these occurs, hold mercaptopurine and monitor labs as above, weekly. Restart at full dose therapy when the transaminase elevation is < Grade 3 (less than 5x ULN), as long as direct bilirubin is < 2 mg/dl.

Exclude infectious hepatitis for persistent (> 1 month) Grade 3 elevations in SGPT/ALT or SGOT/AST above 5x ULN.

Consider discontinuing trimethoprim/sulfamethoxazole (TMP/SMX) in favor of an alternative approach to Pneumocystis prophylaxis and holding/modifying all other potentially hepatotoxic medications.

Cycle 2:

Patients who tolerate cycle 1 without DLT may have the option to repeat this cycle once. Cycle 2 may start on Day 15 – 22 of cycle 1.

